#### 5.2.1. Description.

Venetoclax is a selective inhibitor of BCL-2 protein. It is a light yellow to dark yellow solid with the empirical formula C45H50ClN7O7S and a molecular weight of 868.44. Venetoclax has very low aqueous solubility. Venetoclax is described chemically as 4-(4-{[2-(4-chlorophenyl)-4,4-dimethylcyclohex-1-en-1-yl]methyl}piperazin-1-yl)-N-({3-nitro-4-[(tetrahydro-2H-pyran-4-ylmethyl)amino]phenyl}sulfonyl)-2-(1H-pyrrolo[2,3-b]pyridin-5-yloxy)benzamide) and has the following chemical structure:

Page | 16 04/25/2024

**Figure 4**: Structure of Venetoclax: a selective and orally bioavailable small-molecule inhibitor of BCL-2.

Venetoclax tablets for oral administration are supplied as pale yellow or beige tablets that contain 10, 50, or 100 mg venetoclax as the active ingredient. Each tablet also contains the following inactive ingredients: copovidone, colloidal silicon dioxide, polysorbate 80, sodium stearyl fumarate, and calcium phosphate dibasic. In addition, the 10 mg and 100 mg coated tablets include the following: iron oxide yellow, polyvinyl alcohol, polyethylene glycol, talc, and titanium dioxide. The 50 mg coated tablets also include the following: iron oxide yellow, iron oxide red, iron oxide black, polyvinyl alcohol, talc, polyethylene glycol and titanium dioxide.

# 5.2.2. Dosage and Administration.

Venetoclax is an oral medication that is taken continuously once daily with food and water: patients should take tablets with a meal and water at approximately the same time each day. Tablets should be swallowed whole and not chewed, crushed, or broken prior to swallowing. Tablet may be split in half to allow for more accurate dosing. It will be administered according to the following dose schedule (**Table 2**). Compliance will be verified by counting the tablets provided per day during clinic visits.

Table 2: Venetoclax ramp-up dose schedule

Dosing	Day 1	Day 2	Day 3 and onward
Adolescent or adult patients	100 mg/day	200 mg/day	400 mg/day

Page | 17 04/25/2024

**Tables 3 and 4** provide recommendations for management and potential interactions with CYP3A and P-gp inhibitors and examples of drugs that interact with venetoclax.

Concomitant use of venetoclax with *strong* CYP3A inhibitors and inducers at initiation and during the ramp-up phase is not recommended due to the potential for increased risk of tumor lysis syndrome (TLS). If use of a strong CYP3A inhibitor is deemed necessary, Venetoclax dose should be modified according to **Table 3**. Concomitant use of venetoclax with strong or moderate CYP3A inducers is not recommended throughout the study period. Concomitant strong or moderate CYP3A or P-gp inhibitors must have reached steady state prior to venetoclax initiation and must also not be discontinued until after the initiation and ramp-up phase of venetoclax. If a concomitant strong or moderate CYP3A inhibitor or P-gp inhibitor is discontinued after the initiation and ramp-up phase, increase venetoclax to 400 mg/day 2 to 3 days after discontinuation of the inhibitor. Reduce venetoclax once-daily dose by 50% for patients with severe hepatic impairment (Child-Pugh C); monitor these patients more closely for signs of toxicity.

Table 3: Management of potential venetoclax interactions with CYP3A and P-gp inhibitors\*

Coadministered drug	Initiation and ramp-up phase	Steady daily dose(after ramp-up phase)
Posaconazole	Start at 10 mg on day 1, followed by 20 mg on day 2, 50 mg on day 3, and 70 mg on day 4	Reduce the venetoclax dose to 70 mg
Other strong CYP3A inhibitor	Start at 10 mg on day 1, followed by 20 mg on day 2, 50 mg on day 3, and 100 mg on day 4	Reduce the venetoclax dose to 100 mg
Moderate CYP3A inhibitor	Reduce the venetoclax dose by at least 5	.n%
P-gp inhibitor	heduce the vehicloclax dose by at least 3	00/0

\*Consider alternative medications or reduce the venetoclax dose as described in this table. CYP3A=cytochrome P450; P-gp=P-glycoprotein.

Table 4: Examples of CYP3A and P-gp inhibitors/inducers\*

Coadministered drug	Name	
Other strong	Clarithromycin, Conivaptan, Diltiazem, Indinavir, Itraconazole, Ketoconazole,	
CYP3A inhibitor	Lopinavir, Ritonavir, Telaprevir, Voriconazole, Posaconazole	
Moderate CYP3A	Aprepitant, Cimetidine, Ciprofloxacin, Cyclosporine, Dronedarone,	
inhibitor	Erythromycin, Fluconazole, Isavuconazole, Verapamil	
	Amiodarone, Carvedilol, Clarithromycin, Cyclosporine, Dronedarone,	
P-gp inhibitor	Itraconazole, Ketoconazole, Quinidine, Ranolazine, Ritonavir, Verapamil,	
	Posaconazole	
Strong CYP3A	Carbamazepine, Phenytoin, Rifampin, St. John's wort	
inducer	Carbamazepine, Frienytom, Knampin, St. John S Wort	
Moderate CYP3A	Bosentan, Efavirenz, Etravirine, Modafinil	
inducer	Busentan, Elavirenz, Etravirine, ivioualinii	

\*This is not an exhaustive list and is intended only to complement, not replace, clinical judgment during treatment of patients with venetoclax. Please refer to the FDA website for more examples.

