#### 6.2. Recommended Venetoclax Dose Modification.

Interrupt dosing, reduce number of days, or reduce dose for toxicities. Treatment modifications for venetoclax related toxicities will be performed as per the respective summaries of product characteristics (SmPC). As CB-103 and venetoclax do not have overlapping toxicity, dose modification of CB-103 is independent of venetoclax dose modification: treatment modifications for CB-103 related are described in **Section 6.1.** 

See the following **Tables 14a and 14b** for dose modifications for hematologic and other toxicities related to **venetoclax**. For patients who have had a dosing interruption greater than 1 week reassess for risk of TLS to determine if reinitiation with a reduced dose is necessary.

Table 14a: Recommended Dose Modifications of Venetoclax for Toxicitiesa

Event	Occurence	Action
	•	Tumor Lysis Syndrome
Blood chemistry		Withhold the next day's dose. If resolved within 24 to 48 hours of last dose, resume at the same dose.
changes or symptoms	Any	For any blood chemistry changes requiring more than 48 hours to resolve, resume at a reduced dose.
suggestive of TLS		For any events of clinical TLS b , resume at a reduced dose following resolution.
		Non-Hematologic Toxicities
Grade 3 or 4 non-		Interrupt venetoclax. Once the toxicity has resolved to Grade 1 or baseline level, VENCLEXTA therapy may be resumed at the same dose. No dose modification is required. Consider decreasing treatment days.
hematologic toxicities	2nd and subsequent occurrences	Interrupt venetoclax. Follow dose reduction guidelines in Table 14b when resuming treatment with Venetoclax after resolution. Consider decreasing treatment days. A larger dose reduction may occur at the discretion of the physician.
		Hematologic Toxicities
Grade 3 or 4 neutropenia with infection or fever; or	1st occurrence	Interrupt venetoclax. To reduce the infection risks associated with neutropenia, granulocyte-colony stimulating factor (G-CSF) may be administered with Venetoclax if clinically indicated. Once the toxicity has resolved to Grade 1 or baseline level, Venetoclax therapy may be resumed at the same dose. Consider decreasing treatment days.

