Grade 4 hematologic toxicities (except lymphopenia)	occurrences	Interrupt venetoclax. Consider using G-CSF as clinically indicated. Follow dose reduction guidelines in Table 14b when resuming treatment with Venetoclax after resolution. Consider decreasing treatment days. A larger dose reduction may occur at the discretion of the physician.

Consider decreasing treatment days for those patients with toxicities. Treatment could be decreased from 28 days to 21, 14 or 7 days, depending on the PI. Discontinue venetoclax for patients who require dose reductions to less than 25% of the scheduled dose for more than 2 weeks.

aAdverse reactions were graded using NCI-CTCAE v.5.0 guideline.

bClinical TLS was defined as laboratory TLS with clinical consequences such as acute renal failure, cardiac arrhythmias, or sudden death and/or seizures.

Protocol 2021-0547 4/25/2024

**Table 14b:** Dose reduction for toxicity during Venetoclax treatment

Dose at Interruption, mg	Restart Dose, mg a
400	300
300	200
200	100
100	50
50	20
20	10

<sup>aDuring the ramp-up phase, continue the reduced dose for 1 week before increasing the dose.

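### Section 5.2.2 sends venetoclax back to 400 mg/day when an interacting inhibitor stops after ramp-up, with no exception for a toxicity reduction already in force

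*Combined protocol and SAP*

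**What the plan says.** Three parts of the combined protocol and SAP bear on this.

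**Interaction rule (Section 5.2.2).** Table 2 reaches 400 mg/day on day 3. Table 3 lowers venetoclax when an interacting drug is given. After ramp-up with a strong CYP3A inhibitor other than posaconazole, the entry is "Reduce the venetoclax dose to 100 mg". If a strong or moderate CYP3A inhibitor or a P-gp inhibitor is stopped after ramp-up, the instruction is to "increase venetoclax to 400 mg/day 2 to 3 days after discontinuation of the inhibitor". The paragraph does not refer to Section 6.2.

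**Toxicity rule (Section 6.2).** Table 14a requires a lower dose in several situations:
- For grade 3 or 4 non-hematologic events, the Table 14b reductions apply at "2nd and subsequent occurrences".
- For the hematologic events it lists, a repeat occurrence also leads to Table 14b "when resuming treatment with Venetoclax after resolution".
- For tumor lysis the rule applies at any occurrence: "For any blood chemistry changes requiring more than 48 hours to resolve, resume at a reduced dose". After clinical tumor lysis the patient is to "resume at a reduced dose following resolution".

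Table 14b steps down 400, 300, 200, 100, 50, 20, 10 mg. Its footnote is the only text on raising a reduced dose, and it is confined to ramp-up: "During the ramp-up phase, continue the reduced dose for 1 week before increasing the dose". Section 6.2 does not mention inhibitor withdrawal.

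**General provisions.** Section 4.3 allows dose changes for expected or observed unacceptable toxicity at the physician's discretion. Section 8.10 requires investigator approval of dose changes when an outside physician gives care.

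**The concern.** Two separate reasons can lower a patient's venetoclax dose: an interacting drug and toxicity. Stopping the interacting drug removes only the first. Section 5.2.2 nevertheless states the next dose as a fixed number, the unreduced scheduled dose, instead of the dose the patient would be on without the interaction. A patient with both reasons would have both undone at once.

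At stake is the safety of individual patients who have already had toxicity that called for a lower dose. A prescriber following the more specific sentence would exceed that dose without anything in the section prompting a check.

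**Working it through.** The plan gives no figure to reproduce here. The check is a comparison of text, plus dose ratios.

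**1. Is there an exception or an order of precedence?**

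| Place | Sets a dose after the inhibitor stops? | Mentions the other rule? |
|---|---|---|
| Section 5.2.2 | Yes: 400 mg/day after 2 to 3 days | No |
| Section 6.2, Tables 14a and 14b | No | No |
| Table 14b footnote | No; ramp-up only | No |
| Section 4.3 | No; general permission to modify | No |

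The only other dose limit in the same part of Section 5.2.2 is a halving for severe hepatic impairment, which is not a toxicity reduction. No exception is stated anywhere.

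**2. Can the sequence arise?** The after-ramp-up column of Table 3 tells the prescriber to reduce an established dose, so the plan contemplates an inhibitor being added after ramp-up. A patient can therefore be reduced for toxicity, then receive an inhibitor, then stop it.

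**3. Size.** The inputs are the 400 mg/day target (Section 5.2.2), the 100 mg dose with a strong inhibitor (Table 3), and the 300 and 200 mg steps (Table 14b).

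Ratio = literal target ÷ toxicity-adjusted dose before the inhibitor.
- One step: 400 → 300 mg (toxicity) → 100 mg (inhibitor) → 400 mg (inhibitor stops). Ratio = 400/300 = 1.33.
- Two steps: 400 → 300 → 200 mg (toxicity) → 100 mg (inhibitor) → 400 mg. Ratio = 400/200 = 2.0.

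The ratio compares 400 mg with the pre-inhibitor dose, so it does not depend on which Table 3 row applied in between. The rise from 100 to 400 mg in a patient with no toxicity reduction is the intended reversal of the interaction adjustment and is not criticised.

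**4. Reduction made while on the inhibitor.** A patient at 100 mg on a strong inhibitor who is cut one step goes to 50 mg (Table 14b). The literal target is again 400 mg. Whether the patient is still on venetoclax by then depends on this rule: "Discontinue venetoclax for patients who require dose reductions to less than 25% of the scheduled dose for more than 2 weeks".
- If the scheduled dose means 400 mg: 50/400 = 12.5%, below 25%, so the inhibitor would have to stop within 2 weeks of the cut.
- If it means 100 mg: 50/100 = 50%, and treatment continues.

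The documents give no dose for this patient once the inhibitor stops, so no ratio to a protocol dose can be formed.

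**The case against.** The strongest reply is that the two sections should be read together. Section 5.2.2 handles interactions and Section 6.2 handles toxicity. Nothing in Section 6.2 ends a reduction because an inhibitor stops, so a sensible prescriber would keep it. Section 4.3 already permits that, since it covers expected as well as observed toxicity. Section 5.2.2 describes its interaction tables as recommendations. Section 8.10 adds investigator approval under outside care. Section 6 also refers to the venetoclax product characteristics, which may settle the matter but are not in the documents.

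Much of this stands as a limit on the practical effect. It does not supply the exception. The permission in Section 4.3 does not alter an instruction that names a dose and a time, Section 8.10 reaches only outside care, and a source not in the documents cannot be credited.

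A second reply is that Section 5.2.2 expects inhibitors to be at steady state before venetoclax begins, so the 400 mg sentence is meant for patients who ramped up on an inhibitor. That may be the intent. The sentence is not limited to those patients, however, and Table 3 provides for adjustment after ramp-up.

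Three stronger readings are tempting, and the documents do not support them:
- **That Section 5.2.2 takes precedence over Section 6.2.** No order of precedence is set. The override is only what the sentence says when read alone.
- **That a patient cut while on the inhibitor receives twice the correct dose.** This takes 200 mg (50/100 × 400) as correct, but proportional conversion appears nowhere in the plan. It also fits Table 14b poorly: the posaconazole dose of 70 mg has no row there.
- **That tumor lysis is the main hazard.** Section 5.2.3 warns of chemistry changes at each dose increase but places the risk in the initial ramp-up, while this instruction applies afterwards. A cut made in ramp-up may already have been reversed under the Table 14b footnote.

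**Conclusion.** The point holds as a minor safety correction. Section 5.2.2 gives an unconditional target of 400 mg/day. Followed as written, it takes a patient reduced to 300 or 200 mg for toxicity to 1.33 or 2 times that dose once the inhibitor stops.

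This rests on three assumptions: the sentence is applied literally, an inhibitor may be started after ramp-up as Table 3 implies, and the reduction follows Table 14b. The tumor lysis rows of Table 14a call for a reduced dose without giving its size, so the ratios for those patients could differ.

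The number of patients affected is unknown. The sequence needs a toxicity reduction, then an inhibitor, then its withdrawal while venetoclax continues, which is probably rare among at most 30 patients. The design inputs in Section 12 do not involve this rule, so no endpoint definition, stopping boundary or operating characteristic changes.

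**What to change.** Amend the sentence in Section 5.2.2 so that, 2 to 3 days after the inhibitor stops:
- venetoclax returns to the dose in use before the inhibitor, or to 400 mg/day if venetoclax was started on the inhibitor, provided in either case that no toxicity reduction was made while on the inhibitor;
- if such a reduction was made, the investigator sets a resumption dose below the one that would otherwise apply;
- any later increase needs investigator approval.

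Under this wording the patients in step 3 of the check return to 300 and 200 mg. The patient in step 4 who was started on the inhibitor resumes below 400 mg, at a dose the investigator chooses. No conversion formula is needed.

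The cost is one or two sentences in an amendment. The downside is that a few patients remain on a lower venetoclax dose after the inhibitor stops, which may cost some activity.

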# 5.2.3. Risk Assessment and Prophylaxis for Tumor Lysis Syndrome (TLS)

Venetoclax can cause rapid reduction in tumor and thus poses a risk for TLS in the initial rampup phase. Changes in blood chemistries consistent with TLS that require prompt management can occur as early as 6 to 8 hours following the first dose of venetoclax and at each dose increase.

Page | 18 04/25/2024

The risk of TLS is a continuum based on multiple factors, including tumor burden and comorbidities. Perform tumor burden assessments, including radiographic evaluation (e.g., CT scan), assess blood chemistry (potassium, uric acid, phosphorus, calcium, and creatinine) in all patients and correct pre-existing abnormalities prior to initiation of treatment with venetoclax. Reduced renal function (creatinine clearance [CrCl] <80 mL/min) further increases the risk.

Patients with ALL at high risk of tumor lysis should be assessed rapidly for evidence of symptomatic hyperleukocytosis, tumor lysis syndrome, and coagulopathy. Suggested initial studies, obtained prior to initiating antileukemia therapy, may include a complete blood count (CBC), prothrombin (PT) and activated partial thromboplastin times (aPTT)and serum electrolytes, including creatinine, BUN, uric acid, phosphorus, and calcium. Continued monitoring of these studies should be carried out at suitable intervals until abnormalities have resolved or the risk has abated.

Recommended TLS prophylaxis based on Tumor Burden from clinical trial data (consider all patient co-morbidities before final determination of prophylaxis and monitoring schedule) is shown in **Table 5**:

Table 5: TLS Prophylaxis

Tumor Burden		Prophylaxis		
		Hydration	Anti-hyperuricemics	
Low	Any LN <5cm AND ALC <25 x10°/L	Oral (1.5-2 L)	Allopurinol	
Medium	All LN >5cm to <10cm AND ALC $\geq$ 25 x10  /L	Oral (1.5-2 L) and consider additional intravenous	Allopurinol	
High	Any LN ≥10cm OR ALC ≥25 x10  /L AND any LN ≥5cm	Oral (1.5-2 L) and intravenous (150- 200 mL/hr as tolerated)	Allopurinol: consider rasburicase if baseline uric acid is elevated	

ALC = absolute lymphocyte count; LN = lymph node.

Administer intravenous hydration for any patient who cannot tolerate oral hydration.

Start allopurinol or xanthine oxidase inhibitor 2 to 3 days prior to initiation of venetoclax.

Evaluate blood chemistries (potassium, uric acid, phosphorus, calcium, and creatinine); review in real time.

For patients at risk of TLS, monitor blood chemistries at 6 to 8 hours and 24 hours at each subsequent ramp-up dose.

**5.2.4. Drug Preparation, Storage and Handling.** Detail drug preparation instructions are provided in the manufacturer's full prescribing information brochure. Unused portions of the study drug will be discarded properly as per the institutional policies.

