#### 3. STUDY POPULATION

#### 3.1. Inclusion Criteria:

**3.1.1.** Adolescent (12 to 18 years) and adult (19 to 60 years) patients who have relapsed or refractory T-cell lymphoblastic leukemia (T-ALL) or T-Cell lymphoblastic lymphoma (T-LBL) according to 2017 WHO classification [29] and NCCN v1 2021 [30]:

Patients must have  $\geq 5\%$  blasts in the bone marrow as assessed by morphology on standard bone marrow biopsy and aspirate or less than 5% blasts in the bone marrow in presence of extramedullary relapse, excluding isolated central nervous system (CNS) relapse. However, if an adequate bone marrow sample cannot be obtained, patients may be enrolled if there is unequivocal evidence of leukemia with  $\geq 5\%$  blasts in the peripheral blood.

- **3.1.2.** Patients are eligible independently of Notch pathway activation in the leukemic blasts: however, a fresh marrow/blood sample must be obtained before starting the study treatment to classify the patients as being either Notch positive or negative.
- **3.1.3.** Leukemic blasts must express of at least 2 of the following immune phenotyping: CD1a, CD2, CD3, CD4, CD5, CD7, CD8, CD34, TCR $\alpha$ B, TCR $\gamma$ S, cyCD3
- **3.1.4.** Patients have adequate performance status (ECOG ≤2) for patients ≥16 years old, Lansky score >50 for patients <16 years old.
- **3.1.5.** Patients must be 12 to 60 years of age inclusive when signing the informed consent. For patients < 18 years of age, parent or legally authorized representative (LAR) should be willing and able to give informed consent. Non-English speaking patients are eligible for whom consent process will follow institutional guidelines.
- **3.1.6.** Patients with CNS disease are eligible.
- **3.1.7.** Patients must have adequate organ function and laboratory results (obtained within 14 days of enrollment):
  - **3.1.7.1.** Direct bilirubin  $\leq 2$  x upper limit of normal (ULN).
  - **3.1.7.2.** Serum creatinine  $\leq$  1.5 x ULN; or if serum creatinine > 1.5 x ULN, then serum creatinine clearance (CrCl)  $\geq$  50 mL/min (estimated by Cockcroft-Gault formula).
  - **3.1.7.3.** Alanine aminotransferase (ALT) and/or aspartate aminotransferase (AST)  $\leq$ 3 x ULN;  $\leq$ 5 x ULN in case of suspected leukemic liver involvement

Page | 9 04/25/2024

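### The tumour lysis prophylaxis classes in Table 5 overlap and leave gaps: among patients with nodes Medium is wholly contained in High, and at least two node/lymphocyte profiles fall in no class

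*Combined protocol and SAP*

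**What the plan says.** Section 5.2.3 grades tumour burden in Table 5 by lymph node (LN) size and ALC (×10⁹/L):

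- **Low:** "Any LN <5cm AND ALC <25". Oral hydration and allopurinol.
- **Medium:** "All LN >5cm to <10cm AND ALC" of 25 or more. Hydration is "Oral (1.5-2 L) and consider additional intravenous", with allopurinol.
- **High:** "Any LN ≥10cm OR ALC ≥25" combined with any node of 5 cm or more. Oral hydration plus intravenous fluid at 150-200 mL/hr as tolerated, with allopurinol, and "consider rasburicase if baseline uric acid is elevated".

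The table is introduced as a recommendation, with the instruction to "consider all patient co-morbidities before final determination of prophylaxis and monitoring schedule". Below it stands a rule for everyone: "Administer intravenous hydration for any patient who cannot tolerate oral hydration". Neither section 5.2.3 nor any other section says which row governs when two are met, or assigns a class to a patient who meets none.

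**The concern.** A tiered prophylaxis table should put each patient in one tier. Here the Medium row joins its two conditions with AND, while the High row already covers ALC of at least 25 with a node of 5 cm or more. Medium therefore adds nothing for patients with nodes, and the intermediate burdens that a middle tier would be expected to hold (one criterion raised, the other not) are left out.

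Timing gives this practical weight. Section 5.2.3 warns that chemistry changes may appear 6 to 8 hours after the first venetoclax dose and after each increase, and Table 2 goes from 100 to 400 mg by day 3. Intravenous hydration has to be decided before dosing. A treating physician with a patient in the overlap finds two intensities. One with a patient in a gap finds no row-specific advice on additional intravenous fluid or rasburicase.

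**Working it through.** There is no planned figure to reproduce; this is a check of the row definitions.

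**Inputs.** The three rows of Table 5, and section 3.1.1, which admits patients on at least 5% "blasts in the bone marrow as assessed by morphology on standard bone marrow biopsy and aspirate" and does not require enlarged nodes. Patients without nodes are therefore eligible and must be classified too.

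**Step 1: overlap.** Suppose a patient has at least one node and meets Medium. All nodes then exceed 5 cm, so some node is 5 cm or more. ALC is at least 25. That is the second arm of High. The order in which AND and OR are read in High makes no difference, because a node of 10 cm or more is also 5 cm or more.

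**Step 2: the exception.** With no nodes, a condition on all nodes is met by default. A node-free patient with ALC of at least 25 can thus be read as Medium without being High. No other patient is Medium alone.

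**Step 3: all profiles.** Node sizes fall in three bands: <5, 5 to <10 and ≥10 cm. A patient may have nodes in any combination of bands or none, giving 2³ = 8 combinations. With ALC <25 or ≥25 there are 8 × 2 = 16 profiles. The word *any* in the Low row may mean every node or at least one node, and this matters only when ALC is below 25.

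| Bands present (cm) | ALC <25, Low = every node | ALC <25, Low = at least one node | ALC ≥25, either reading |
|---|---|---|---|
| No nodes | Low | **no row** | Medium |
| <5 only | Low | Low | **no row** |
| 5 to <10 only | **no row** | **no row** | **Medium and High** |
| ≥10 only | High | High | High |
| <5 and 5 to <10 | **no row** | Low | High |
| <5 and ≥10 | High | **Low and High** | High |
| 5 to <10 and ≥10 | High | High | High |
| All three | High | **Low and High** | High |

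An example of the Low/High overlap is nodes of 3 and 12 cm with ALC 10.

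**Step 4: counts.**

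| Reading of Low | One row | No row | Two rows | Total |
|---|---|---|---|---|
| Every node | 12 | 3 | 1 | 16 |
| At least one node | 10 | 3 | 3 | 16 |

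Medium alone applies to 1 of 16 under either reading, the node-free profile with ALC ≥25. If the rows are taken to need at least one node, Medium alone applies to 0 of 16. The number with no row is then 3 + 2 = 5 (every node) or 3 + 1 = 4 (at least one node).

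**Step 5: the 5 cm boundary.** Medium is printed as above 5 cm, so a node of exactly 5.0 cm is not Medium. With ALC ≥25 it is High only. With ALC <25 and no other node it meets no row. The band count places it with 5 to <10 cm; the overlap and the gaps stand.

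**Step 6: finer grid.** Take smallest and largest node from 0.5 to 15 cm in 0.5 cm steps (30 × 31 / 2 = 465 pairs), plus no nodes, crossed with ALC 0 to 100 in steps of 5 (21 values): 466 × 21 = 9,786 points. Medium with nodes covers 45 size pairs (9 sizes, 5.5 to 9.5 cm) × 16 ALC values = 720 points, and all 720 also meet High. The other 16 Medium points are node-free.

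**The case against.** The strongest reply is that the table is not meant as a strict classifier. Section 5.2.3 calls tumour lysis risk a continuum, labels the table a recommendation, and leaves the final decision to the clinician. Medium and High do not contradict each other, since giving intravenous fluid satisfies both, and a physician would ordinarily follow the higher row.

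Patients in a gap are not unprotected. Outside the rows, section 5.2.3 calls for assessment of tumour burden and chemistry, correction of abnormalities, allopurinol 2 to 3 days before venetoclax, and intravenous fluid when oral fluid is not tolerated. It also asks for rapid assessment and continued monitoring of ALL patients at high lysis risk, and for those at risk it adds chemistry at 6 to 8 and 24 hours at subsequent ramp-up doses. Table 14a withholds venetoclax for chemistry changes. Section 7 refers supportive care to departmental standards and allows hydroxyurea. Section 8 admits patients for Cycle 1 days 1-7. Finally, profile counts say nothing about how many patients are affected, and the node-free Medium case rests on a literal reading that a clinician may not adopt.

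All of this bears on weight, and it does limit the likely harm. It does not repair the table. None of these provisions assigns a class or supplies the row-specific advice, and withholding venetoclax acts only after chemistry has changed. Judgement can adjust a class, but here it would have to supply a missing one.

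**Conclusion.** The point holds. For patients with nodes the three-tier table works as two tiers. All nodes <5 cm with ALC ≥25, and all nodes >5 to <10 cm with ALC <25, meet no row under either reading of Low. A third gap depends on that reading: mixed nodes <5 and 5 to <10 cm with ALC <25 (every node), or no nodes with ALC <25 (at least one node). Under the second reading Low also overlaps High.

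The size is 3 of 16 profiles with no row and 1 or 3 with two, assuming that a node-free patient satisfies a condition on all nodes; otherwise 4 or 5 have no row. The documents give no distribution of node size or ALC, so the share of patients cannot be stated.

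This is a bounded fault in safety guidance that should be corrected. It does not touch the endpoints, stopping boundaries, sample size or analysis. Prescribing information is linked from section 5.4 but was not available, so whether it settles the classification is unknown.

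**What to change.** Rewrite the three rows at the existing cut-offs:

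- **Low:** no node ≥5 cm (including no enlarged nodes) and ALC <25.
- **Medium:** High not met, and either any node of 5 to <10 cm or ALC ≥25.
- **High:** unchanged, that is any node ≥10 cm, or ALC ≥25 with any node ≥5 cm.

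Add a line that the higher class applies if more than one is met.

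On the 16 profiles this gives Low 2, Medium 4 and High 10, which sum to 16, with none in two rows or in no row. All 9,786 grid points also fall in exactly one class. Node-free patients become Low or Medium according to ALC.

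Moving Medium from AND to OR is a clinical choice that the documents do not settle, so the sponsor's clinical team should confirm it or assign the uncovered profiles another way.

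The cost is a one-table correction in the next amendment and a notice to the treating team at the single site. The downside is that intravenous hydration will be considered or given for some additional patients.
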